Expected Impact in Reducing Comorbidity among Persons with OUD. As most substance use treatment facilities are unable to address anxiety and depressive disorders and the treatments that are available to address anxiety and depressive disorders among persons with opioid disorders are not broadly disseminated, the creation of a low-cost, scalable treatment to address anxiety and depressive disorders within this population could have an impact on the total distress and functional impairment caused by anxiety and depression. There is reason to suspect that uptake of these interventions will be substantial given that: (1) patients in medication-treatment for OUD are highly willing to participate in stress-reduction treatments and (2) high anxiety levels are associated with a greater willingness to participate in treatment (Barry et al., 2011). As importantly, given the causal nature of anxiety and depression on cravings and opioid-seeking behaviors, effective treatment of anxiety and depressive symptoms may also result in decreased cravings and opioid use behaviors among persons receiving treatment. Thus, the development of an efficacious technology-based intervention could provide scalable stepped-care to a vulnerable population and also enhance outcomes for OUD.

B. INNOVATION

The widespread high comorbidity and untreated anxiety and depressive disorders among persons receiving treatment for OUD highlights the need for the development of new scalable treatments for anxiety and depressive symptoms within this population. Thus, the overarching innovation of this study is evaluating a scalable intervention treating anxiety and depressive symptoms among persons receiving treatment for OUD. This intervention involves a brief video from our PI explaining differing relaxation and mood control techniques as well as the science behind these. Please see attached for an

example: https://www.dropbox.com/s/o8ncxhlvp8y1u2/Exercise_Intervention_Video_Example.mov?dl=0. We will be covering techniques such as improving physical activity, muscle relaxation, nutrition and more. This study has the potential to reduce anxiety and depressive symptoms, increase the efficacy of medication treatment for OUD, and potentially decrease the long-term relapse rates and deleterious outcomes (i.e., given that anxiety and depressive disorders are associated with an increased risk of relapse). Specific innovations include:

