Main Study: Participants will complete the main consent form. Participants will complete self-report assessments on their anxiety symptoms, depressive symptoms, opioid cravings, and opioid use behaviors. Participants will be randomized to a smartphone-based digital intervention or waitlist control condition. The control group can receive the intervention once they have completed the one-month follow up section of the study if they would like it. The digital intervention will be designed to treat participants' anxiety and depressive symptoms, and participants will be asked to use the intervention four times per week for four weeks (16 digital sessions). Participants will complete post measures and one-month follow-up measures on anxiety symptoms, depressive symptoms, opioid cravings, and opioid use behaviors. The Precision Dx12-panel test cups (manufactured by American Screening Complete Drug Test Solutions) will be mailed to participants. Participants will also be asked to complete five urine tests to detect substance use (amphetamines, barbiturates, benzodiazepines, cocaine, ecstasy, marijuana, methamphetamine, opioids, oxycodone, and propoxyphene) across the study (1 at pre-digital intervention, 1 during the digital intervention, 1 post-digital intervention, 1 between post and follow-up of the digital intervention, and 1 at the 1-month follow-up of the digital intervention). Participants will be instructed when to complete each urine test and will be asked to take a photo of the back the label of each test showing the results to the experimenters and to text these photos to a Google Voice Number maintained by the experimenters. Both the digital intervention group and the control group will receive the same follow-up assessments and be asked for the urine samples. Following the study, the control group will be able to access the intervention and have access to the study team for support.

The Link for the intervention videos is below:

<https://drive.google.com/drive/folders/1aGv-d85VnuriTcta9dkRt6OjizcMHRf2?usp=sharing>

4. Analysis

Describe any qualitative tests and measures as well as quantitative methods:

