Analyses. To test feasibility for **Hypothesis 1**, we will determine whether we can achieve the targeted enrollment ($N = 80$) and whether the average number of digital sessions is significantly higher than 50% based on multilevel binomial test nesting individual session completion rates within persons. To test **Hypothesis 2**, the current proposal will use intent-to-treat analyses employing multilevel modeling to examine moderation of change across time from pre to post, and post to follow-up. Based on power analyses, we will be well-powered to test the effects of the intervention (3-5 data points per person \times 80 participants = 180-300 \times 80% adherence = 144-240 data points total).

5. Study Progress Monitoring

Note: appropriate monitoring may include periodic assessment of the following:

- data quality
- timelines
- recruitment and enrollment

Provide a description of the methods which will be used to determine the progress of the study, including periodic assessments of data quality, timelines, recruitment, and enrollment as appropriate:

Recruitment. A population of 3000 adults who are receiving medication treatment for OUD will be recruited from an online study based on Google Adwords advertisements as online recruitment has been shown to be a viable and cost-effective recruitment method for opioid users (Marshall et al., 2018). We are only recruiting from the US.

We will also recruit via Reddit forum as well. Please see the document with the example of the post we would be planning on using.

Six opioid-focused subreddits were initially identified. Subreddits were selected based on their topical focus and their popularity. All were devoted to discussion of opioid use or recovery. In September 2019, the number of Redditors subscribed to each subreddit ranged from 4,000 to 82,000 people. Each subreddit was monitored by multiple moderators, who ensured all posts follow the Reddit community guidelines and remain focused on the topic of interest. All moderators in each of the six subreddits will be contacted by the study team to obtain approval to post the survey description and hyperlink. Moderators will be sent a study information sheet and a link to view the study description.

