There are no high risks or hazardous aspects of the proposed study. Nevertheless, we realize that interventions and assessments may promote increased focus on their mental health symptoms, compared to before they started the study. Research suggests that assessments are associated with *decreases* in MDD symptoms (Bakker & Rickard, 2018; Kauer et al., 2012). To date, the principal investigator has collected data from over 10,000 participants asking them to engage in anxiety and depressive interventions and experienced no known adverse events (Jacobson & Wilhelm, 2019). Given this, although there is a possibility that a subset of persons could react negatively to the intervention, it is also very unlikely to occur. Additionally, referrals for in-person treatment will be offered in the event of worsening suicidality or at the request of participants (see **Clinical Referrals below**). If any participant appears to be in crisis, appropriate action will be taken based on established suicide and crisis assessment protocols. Participants who report concerning levels of symptoms will be highlighted via algorithms as requiring contact and in-person referrals.

2. Adequacy of Protection Against Risks

a. Recruitment and Informed Consent

Recruitment. Recruitment will take place via Google Adwords and Reddit. **Informed consent.** The informed consent prior to the screen will provide information about the nature of the study in its entirety, including both information about the questions asked during the screen, data storage and retention plan, who will have access to this information, and responses to any participant questions. Participants will also be informed of the potential risks, benefits, and measures taken to protect participant confidentiality, and they will be provided an opportunity to ask questions about the study.

b. Protection against Risk

Protection of Privacy. Participants' privacy will be safeguarded by fully informed consent by informing participants what data will be collected, who will have access to this information, and how knowledge of how information collected will be utilized and disseminated (Ziegeldorf, García-Morón, & Wehrle, 2014).

Exclusion of High-Risk Populations. The current study will exclude persons who will be at high risk, specifically those with: (1) active suicidality, (2) psychosis, and (3) bipolar disorder. Treatment referrals will be made to those persons (see **Clinical Referrals below**).

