Clinical Expertise. All research will be overseen by [name] who has a doctorate in clinical psychology.

Availability of the Study Team. [name] will be available to discuss the study or any concerns about the study with participants if requested by the participant. [name] will be available in the event of a clinical emergency, and this availability will be clearly communicated orally and in writing to study participants. Participants will be provided information such as how to reach the investigators in the event of a clinical emergency. Participants will be referred to a treatment resource or a higher level of care if needed (i.e., hospitalization). Participants will be referred to a higher level of care if there is evidence of (1) acute active suicidality with a plan and intent to take one's life within a delineated period of time (i.e. less than 1 year), (2) acute homicidally with a plan or intent to take another's life, or (3) likelihood that they could immediately cause severe bodily harm to themselves or others (see **Clinical Referrals below**).

Ability to Withdraw. Participants may be able to withdraw from the study due to a significantly deteriorating course (e.g., need for hospitalization) or if the PI or participant determines that staying in the study is not in the participant's best interest. All participants who withdraw will be provided referrals for treatment.

Clinical Referrals. All participants will be given the phone number for the National Suicide Prevention Hotline, which is funded by the Substance Abuse and Mental Health Services Administration (SAMHSA). The hotline is staffed 24/7 by licensed mental health providers and is available throughout the United States. For persons not in acute risk who need a referral to outpatient treatment, we will identify referral sources using the Anxiety and Depression Association of America (ADAA), the Association for Behavioral and Cognitive Therapies (ABCT), the American Psychiatric Association, and the American Psychological Association. Each of these organizations maintains an active registry of current psychologists and psychiatrists across the country, many of whom provide the ability to also specify persons specializing in treating anxiety and depression.

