, the study team believes that referring participants to helpful resources is sufficient given the nature of the study. We will not be actively monitoring suicidality throughout the study and will only ask the PHQ-9 at certain points during the study. If participants give concerning responses when questionnaires are administered there will be an automated referral process to initiate resources if persons indicate high suicidal ideation.

Additionally, there is evidence that administering questionnaires such as the PHQ-9 do not increase an individual's likelihood of suicidality. We do not believe that our study questionnaires will increase this likelihood. Again, anyone indicating suicidality in the screening questionnaires will not be eligible for the study. As we are mainly concerned with Opioid Use in our study demographic, we do not anticipate too many participants in our 80 person sample indicating high suicidal ideation, believe that our referral process will be sufficient.

b. Confirm that risks to subjects have been minimized, by use of procedures which are consistent with sound research design and which do not unnecessarily expose subjects to risk:

The study teams believes that they have taken the necessary precautions to ensure the safety of our participants.

Protection of Privacy. Participants' privacy will be safeguarded by fully informed consent by informing participants what data will be collected, who will have access to this information, and how knowledge of how information collected will be utilized and disseminated.¹²⁹ All participants must demonstrate comprehension (full understanding of study details), competence (ability to provide consent), and voluntariness (consent of their own volition) based on their phone calls with the postdoctoral fellow. Following suggestions for fully addressing privacy concerns in digital phenotyping studies, consent will be obtained through verbal discussion with a postdoctoral fellow

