13. Financial impact on participants

a. List the tests, visits, and procedures performed for only research purposes and specify who will pay:

Note: Research procedures may not be billed to a health insurance plan

Participant Recruitment. A total of \$3,000 will be spent on online participant recruitment in the US only. We estimate a total cost of \$10 per participant to recruit 3000 participants, with an estimated enrollment of 2% of persons who complete the screen will enroll in the primary portion of the study.

Precision Dx 12-panel Urine Tests. The Precision Dx 12 Panel Cup test cups will cost a total of \$2,250.00 to purchase (we will need to purchase 300 units, with 25 units per case, we will need to purchase 12 cases with each case costing \$187.50). To save on shipping costs, the five tests will be mailed together to participants in one box. Participants will be asked to send a picture of the results label to save on shipping costs and so that no bodily fluids are traveling via mail. There will be an estimated \$720 in shipping costs.

Participant Remuneration: Participants will be paid \$15 for each pre, post, and follow-up questionnaire assessment and \$15 for each urine test (totaling \$120 per participant). Thus, the total cost requested for participant payment is \$7,200.

14. Compensation or Gifts

Please describe any payments, gifts or reimbursements participants will receive for taking part in the study:

Participants will be compensated via amazon giftcard for each component of the study they complete. They will receive 15 dollars for each questionnaire assessment they complete along with 15 dollars for each completed urine test. Compensation will be pro-rated if participants forget to complete any part of the study: The following information lays out the time points that participants will be compensated. Participants will not be compensated for completing the screening questionnaires.

Before the Digital Intervention: 30 dollars total

- 1) \$15 dollars for completing the self-assessment survey
- 2) \$15 dollars for providing the first urine (after 0 weeks) sample results.

After the Intervention is completed: 45 dollars total

- 1) 15 dollars for completing the post-intervention questionnaire
- 2) \$15 dollars for providing second urine sample (after 2 weeks)
- 3) \$15 dollars for providing third urine sample (after 4 weeks)

At the one-month follow-up: 45 dollars total

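### Participants who deteriorate may leave the study with no further assessment planned, so unequal losses between arms could bias the intent-to-treat result for Hypothesis 2, in either direction

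*Combined protocol and SAP*

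**What the plan says.** - **Analysis.** The Analyses paragraph of Section 4 says Hypothesis 2 will be tested with "intent-to-treat analyses employing multilevel modeling to examine moderation of change across time from pre to post, and post to follow-up". It states no missing-data assumption, no rule for participants who leave and no sensitivity analysis.
- **Withdrawal.** The Ability to Withdraw paragraph, given twice in Section 6 and again in Section 7, says participants may "withdraw from the study due to a significantly deteriorating course (e.g., need for hospitalization) or if the PI or participant determines" that remaining is not in the participant's interest. The only stated consequence is a treatment referral.
- **Assessment times.** Section 3 (Main Study) says: "Participants will complete post measures and one-month follow-up measures on anxiety symptoms, depressive symptoms, opioid cravings, and opioid use behaviors". With the pre assessment this makes three questionnaire occasions. Five urine tests are spread over the same period; Section 14 places them at weeks 0, 2, 4, 6 and 8.
- **Monitoring.** Section 6, after Clinical Referrals: "We will not be actively monitoring suicidality throughout the study and will only ask the PHQ-9 at certain points during the study".
- **Expected harm.** Section 6 (Potential Risks) says "although there is a possibility that a subset of persons could react negatively to the intervention, it is also very unlikely to occur". No rate of withdrawal for deterioration appears anywhere.
- **Nearby statements that do not fill the gap.** Section 4 assumes 80% adherence. The dropout remark in Section 5 concerns screening ineligibility. Section 14 covers only pro-rated payment for missed components.

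**The concern.** Worsening mood, craving or opioid use is the Hypothesis 2 outcome, and the plan also names a worsening course as a reason to leave the study. Loss of data can therefore depend directly on the outcome.

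A likelihood-based multilevel model keeps everyone with any score and is valid if missingness depends only on what was observed. That protection is weak here. A participant who worsens in the four-week intervention period and leaves before the post assessment has only the pre questionnaire and any early urine test. The model then treats that person's later course as typical of the arm.

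The comparison is biased if such losses differ between arms. They could. Only the app arm can react to the app, and the PI, who may decide a withdrawal, presents the intervention (Section 1, Innovation: "This intervention involves a brief video from our PI explaining differing relaxation and mood control techniques"), with no masking of the PI described. Equally, a waitlist arm without the intervention could lose more worsening participants. The arm that loses more of them looks better than it was for everyone randomised, under an intent-to-treat label. Scores not collected after withdrawal cannot be recovered later, and Section 1 intends the result to lead to a larger study.

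**Working it through.** **1. The plan's own figure.** Section 4 counts 3-5 data points × 80 participants as 180-300, and 144-240 after 80% adherence. In fact 3 × 80 = 240 and 5 × 80 = 400; times 0.8 gives 192-320. The printed figures match 60 participants (3 × 60 = 180, 5 × 60 = 300; × 0.8 = 144-240). Aim 2 in Section 2 says 30 per arm; Hypothesis 1 and Section 10 say 80 in total. I use 40 per arm and give 30 as a check. If 80% adherence is applied to participants, 0.2 × 40 = 8 per arm have missing outcomes.

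**2. Inputs.** From the documents: 40 (or 30) per arm, 80% adherence and the three questionnaire occasions. Assumed: unit SD, correlation 0.5 between occasions, k participants in an arm who worsen by d SD and leave before post, and a true mean effect of zero over all randomised. The withdrawn are counted within the 20% missing; the rest are missing at random.

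**3. Formula.** To keep an arm's true mean at zero, the other n − k participants improve by kd/(n − k). Only they are seen at post, so the arm appears to have changed by −kd/(n − k). The bias in app minus control is

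bias = −k_A·d/(n − k_A) + k_C·d/(n − k_C), where negative favours the app.

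**4. Results for n = 40.** The simulated values use a REML random-intercept model with arm-by-occasion terms. The one-sided rows used 2,500 trials each (Monte Carlo error 0.4-0.7 points).

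| Losses, app v control | d | Formula | Simulated bias | Two-sided false positives |
|---|---|---|---|---|
| 1 v 0 | 2 | −2/39 = −0.05 | −0.05 | 5.5% |
| 2 v 0 | 2 | −4/38 = −0.11 | −0.10 | 7.8% |
| 4 v 0 | 1 | −4/36 = −0.11 | −0.11 | 7.5% |
| 4 v 0 | 2 | −8/36 = −0.22 | −0.22 | 14.6% |
| 4 v 2 | 2 | −8/36 + 4/38 = −0.12 | −0.11 | about 7% |
| 4 v 4 | 2 | 0 | near 0 | not tabulated |

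Reversing the arms reverses the sign. With 30 per arm, 3 v 0 and d = 2, the formula gives −6/27 = −0.22 and simulation gives −0.23 SD with 12.8% false positives.

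**5. Other settings.**
- *The same four still assessed* (4 v 0, d = 2): bias 0.00, false positives 4.9%.
- *Leaving just after post* (4 v 0, d = 2): bias near zero at post; about −0.14 SD with about 8% false positives at follow-up.
- *Both arms with the same outcome distribution, the worst-changing 4 of 40 lost from the app arm only*: about −0.13 SD and 12-14% false positives in a baseline-adjusted model (correlation 0.5 to 0.7). Equal 10% losses give almost no bias.
- *Loss depending only on the observed pre score*: no bias. This is the case the multilevel model does handle.

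**6. Scale.** The difference detectable with 80% power (t test, two-sided 5%) is 0.634 SD with 40 per arm. The largest case is 0.22/0.634 = 35% of that; 2 v 0 is 0.10/0.634 = 16%.

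**The case against.** The strongest reply is about timing. The plan does little symptom scoring between assessments, so worsening that the team detects will mostly surface at the post questionnaire, with the score already recorded. The response described for flagged symptoms is contact and referral, not withdrawal. This stands: departure just after post leaves the post comparison almost unbiased, though follow-up is still affected. What remains is hospitalisation or self-initiated exit within four weeks, in a sample that excludes active suicidality, psychosis and bipolar disorder.

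Second, the larger figures need one-sided loss, and the documents do not show that one arm would lose more. That also stands. Both arms are assessed, and Section 6 mentions assessments as well as interventions when it discusses heightened focus on symptoms.

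Third, nothing says that merely stopping the app ends assessment. Both arms have the same follow-up, and payment is per questionnaire and urine test, not per session. That is fair for non-use of the app, but the withdrawal paragraph concerns leaving the study.

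A reader might infer that deteriorating participants must be removed, that they are excluded from the analysis, or that the app's result will be flattered. The documents support none of these. The withdrawal wording is permissive, the multilevel model keeps whatever scores exist, and the direction depends on which arm loses more.

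**Conclusion.** The gap is real: the plan permits withdrawal from the study for a reason tied to the outcome, plans no assessment afterwards, and labels the analysis intent-to-treat. The consequence is conditional. It needs several participants to worsen and leave, unequally between arms, mostly before post. Under the assumed 2 SD worsening the shift is roughly 0.1 SD for a net excess of two losses in one arm and 0.22 SD for an excess of four. One loss, or equal losses, makes no material difference to the estimate.

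The rate, the worsening and the imbalance are all assumptions, and the plan itself expects negative reactions to be very unlikely. The 15% false-positive rate is therefore an upper illustration, not a forecast. A reader might take it as showing that the Hypothesis 2 analysis is invalid; it does not show that. Severity: minor to moderate. It is worth settling before enrolment because the remedy is cheap and lost scores cannot be recovered.

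**What to change.** 1. State that stopping the app does not end study participation. A participant who deteriorates stops the app, is referred as now planned, and is still invited to the remaining questionnaires and urine tests unless they decline, are unable, or the PI judges that the assessments themselves are not in their interest.
2. State that Hypothesis 2 uses all collected data of all randomised participants, by assigned arm, whether or not they stopped the app.
3. For each withdrawal record the date, arm, reason and who decided, and report the counts by arm.
4. Prespecify one simple sensitivity analysis: for participants withdrawn for deterioration with missing scores, assign worse outcomes than the model predicts (for example 2 SD worse), and say whether the conclusion changes.

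**Cost.** A small change to protocol and consent text, one form and one extra analysis. It alters the withdrawal rule slightly, since the PI would judge the app and the assessments separately; the PI's authority to end either, and the participant's right to leave, remain. No extra mailing is needed, because Section 13 says "the five tests will be mailed together to participants in one box". Payments after a withdrawal before week 2 are at most 15 × (2 questionnaires + 4 urine tests) = $90, within the planned 15 × (3 + 5) = $120 per participant. The stated total of $7,200 covers 7,200/120 = 60 participants; 80 would need 80 × 120 = $9,600. That shortfall exists regardless of this change. Some withdrawn participants will still decline, which is why the sensitivity analysis is needed.

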1. Developing a novel technology-based intervention for anxiety and depressive symptoms among those receiving medication treatment for OUD.
2. Evaluating the feasibility of a technology-based intervention for anxiety and depressive symptoms among persons receiving treatment for OUD.
3. Evaluating the efficacy of a technology-based intervention for anxiety and depressive symptoms among persons with OUD.
4. Evaluating the efficacy of a technology-based intervention treating anxiety and depressive symptoms on cravings and opioid use among persons receiving medication treatment for OUD.

2. Objectives and Hypotheses

Aim 1: To test the feasibility and acceptability of the digital intervention designed to treat anxiety and depressive symptoms among persons receiving medication treatments for OUD.

Hypothesis 1: The digital intervention will show feasibility based on the ability to recruit participants (N = 40 within the digital intervention + medication treatment, N = 40 with medication treatment) and demonstrate acceptability of the application with greater than 50% of the intervention sessions completed on average by the treatment group.

Aim 2: To test the efficacy of a digital intervention targeting anxiety and depressive symptoms among persons receiving medication treatment for OUD. Sixty participants receiving medication treatment for OUD will be randomized to receive a digital intervention to treat anxiety and depression (N = 30) or care as usual (N = 30) for a total of four weeks.

Hypothesis 2: The digital intervention app group will experience (a) greater symptom reduction in anxiety and depressive symptoms (based on self-report measures) and (b) decreased opioid cravings and use across a four-week period (based on self-report measures and urine tests).

3. Study Design

Describe all study procedures, materials, and methods of data collection:

Recruitment. A population of 3000 adults who are receiving medication treatment for OUD will be recruited from an online study based on Google Adwords and Facebook advertisements as online recruitment has been shown to be a viable and cost-effective recruitment method for opioid users (Marshall et al., 2018).

We would also like to expand our recruitment efforts to Reddit sub-pages as well. Previous researchers looking at opioid addiction have had success posting in the Reddit forums and we would like to also recruit using this platform.

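### The power claim rests on a data-point count computed for 60 participants but labelled 80, and the plan gives both numbers as its target

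*Combined protocol and SAP*

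**What the plan says.** The Analyses paragraph of Section 4 sets the enrolment target at 80 and then states: "Based on power analyses, we will be well-powered to test the effects of the intervention (3-5 data points per person". It multiplies the 3-5 points by 80 participants, gives the product as 180-300, and ends with "80% adherence = 144-240 data points total". It reports nothing else from the power analyses it mentions.

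The number of participants is stated in several places:

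- **Section 2, Hypothesis 1:** "N = 40 within the digital intervention + medication treatment, N = 40 with medication treatment", that is, 80.
- **Section 2, Aim 2 (efficacy):** "Sixty participants receiving medication treatment for OUD will be randomized to receive a digital intervention to treat anxiety and depression (N = 30", with 30 in the care-as-usual arm, that is, 60.
- **Sections 6 and 10a:** a sample of 80.
- **Section 13, urine tests:** "we will need to purchase 300 units, with 25 units per case", with five tests mailed to each participant.
- **Section 13, remuneration:** $120 per participant, and "the total cost requested for participant payment is" $7,200.
- **Section 13, recruitment:** 3000 people recruited, with an "estimated enrollment of 2% of persons who complete the screen will enroll in the primary portion of the study".

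Section 3 gives the measurement schedule. Questionnaires are completed at pre, post and one-month follow-up. For urine, "Participants will also be asked to complete five urine tests to detect substance use". Section 10b asks for a justification of the sample size, and the answer describes only the advertising channels.

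**The concern.** There are three linked problems. The multiplication is wrong for the N printed in it. The plan gives two different numbers to be randomised, and the wrong product fits the one it does not name. The product is also the only support shown for the power claim, although a total of data points does not measure power for Hypothesis 2. That hypothesis compares change between arms. Its precision depends mainly on the number of people per arm, the effect size relative to the SD, the within-person correlation and the missing data.

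N fixes how many people are randomised, whether Hypothesis 1's enrolment target is met, and how many test cups are bought for a Hypothesis 2 outcome. If 60 are enrolled, Aim 2's number is reached while Hypothesis 1's is missed, so success could be judged afterwards against either figure.

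**Working it through.** **The plan's own figures.** Inputs from Section 4: 3-5 points per person, N = 80, 80% adherence. The formula is points per person × N, then × 0.8.

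| | 3 points | 5 points | 3 points × 0.8 | 5 points × 0.8 |
|---|---|---|---|---|
| Printed | 180 | 300 | 144 | 240 |
| N = 80 | 240 | 400 | 192 | 320 |
| N = 60 | 180 | 300 | 144 | 240 |

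None of the printed figures matches N = 80; all four match N = 60. The two ends of the range also belong to different outcomes: three occasions for questionnaires, five for urine tests.

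**The N implied by Section 13.**

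- Cups: 300 / 5 = 60. For 80 people, 300 / 80 = 3.75 cups each, against five planned.
- Payments: $7,200 / $120 = 60.
- Enrolment yield: 0.02 × 3000 = 60. This is weaker evidence, because the same item budgets $3,000 at $10 per person for 3000 people, and 3000 × $10 = $30,000.

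**Scale of the power question (illustration only).** The documents give no alpha, effect size or correlation. Assumptions: two-sided 5%, two equal arms, one pre-post comparison of a continuous outcome, noncentral t with 2n − 2 degrees of freedom and noncentrality d × √(n/2), where n is the number per arm and d is in SDs of the change score. Reading 80% adherence as 80% of participants contributing gives 0.8 × 40 = 32 or 0.8 × 30 = 24 per arm.

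| Per arm | Power, d = 0.3 | Power, d = 0.5 | Power, d = 0.8 |
|---|---|---|---|
| 40 (N = 80, no loss) | 26% | 60% | 94% |
| 32 (N = 80, 80% contribute) | 22% | 50% | 88% |
| 30 (N = 60, no loss) | 21% | 48% | 86% |
| 24 (N = 60, 80% contribute) | 17% | 40% | 77% |

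With 80% contributing, 80% power is reached at d = 0.71 (32 per arm) or d = 0.83 (24 per arm).

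**Sensitivity to the pre-post correlation.** Now take d = 0.5 in raw SDs, with correlation r from 0.3 to 0.7. The SD is multiplied by √(2(1 − r)) for change scores, and by √(1 − r²), with 2n − 3 degrees of freedom, for baseline adjustment.

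| Per arm | Change score | Baseline-adjusted |
|---|---|---|
| 40 | 46-81% | 64-87% |
| 32 | 38-72% | 54-79% |
| 30 | 36-69% | 51-76% |
| 24 | 30-59% | 43-66% |

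Under like assumptions at d = 0.5, randomising 60 rather than 80 costs 8-13 percentage points in every case.

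**The case against.** The best defence has four parts.

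- **Power analyses may exist.** Section 4 refers to them, and this form may simply not reproduce them. That is fair: the documents do not show that none was done. They do show that no input or result is reported, so the claim cannot be checked, and the one calculation offered in its place is wrong for its own N.
- **The slip is conservative.** True. For 80 people the correct count is larger than the printed one, so the arithmetic error alone does not weaken the claim.
- **This is in part a feasibility study.** Aim 1 is feasibility, Section 4 calls the intervention a prototype, and Section 1 looks ahead to a later grant. A pilot may leave power out. But Aim 2 sets out to test efficacy and the plan itself asserts adequate power, so the assertion needs support.
- **80 is the dominant number.** It appears in the dedicated enrolment item and in three other sections; only Aim 2 states 60 outright, and the rest is inferred from the budget. Even so, Aim 2 is the current statement of how many will be randomised. Nor can 60 be read as a separate efficacy sample, because the power statement for the intervention's effects uses 80.

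The illustrative power figures also have limits. They are two-occasion comparisons, not the planned multilevel model, which can use partly observed participants. They show scale only.

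**Conclusion.** The concern holds. The printed product is wrong for 80 and exact for 60, and the plan states both 80 and 60 as the number of participants. A change from 60 to 80 that was not carried through would explain this, but that is inference and the contradiction does not depend on it.

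The power claim is unsupported as written, because a data-point count stands in for a power calculation and the inputs that matter are absent. This does not show that the trial is underpowered; that turns on an effect size and a correlation the documents do not give. Across the assumptions tried, power at d = 0.5 runs from 30% to 87%, so the claim depends entirely on choices the plan leaves unstated.

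**What to change.** 1. **Choose one N** and use it in Section 2 (Hypothesis 1 and Aim 2), Section 4, Section 6, Section 10a and Section 13.
2. **Correct the count** for that N, separately for questionnaires and urine tests, and do not present it as power. For 80: 240 and 400, or 192 and 320 at 80%. For 60: 180 and 300, or 144 and 240.
3. **Replace the power claim** in Section 4, and complete Section 10b, with a participant-level statement for a named outcome: participants per arm, alpha, effect size and its source, assumed pre-post correlation, expected loss, and power over a range of these. The team must supply the assumptions. State power for the repeated urine result separately, since a standardised mean difference does not describe it.

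**Cost.** The text changes are wording only.

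If 80 is kept:
- Cups: 5 × 80 = 400, or 16 cases × $187.50 = $3,000, which is $750 more than the $2,250 budgeted.
- Payments: 80 × $120 = $9,600, which is $2,400 more than budgeted.
- Shipping rises as well.
- Screening: at a 2% yield, 80 / 0.02 = 4,000 people must be screened. The extra 1,000 cost $1,000 at the rate implied by the budget ($3,000 / 3000) or $10,000 at the stated $10 each, so that item needs correcting too. Otherwise the yield from 3000 must be 80 / 3000 = 2.67%.

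If 60 is kept, the budgets for cups and payments stand, but Hypothesis 1's enrolment target falls and the mentions of 80 in Sections 4, 6 and 10a must change.
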